## **STUDY DESIGN**

The study is a 5-year, randomized controlled clinical intervention trial at a singular academic medical center.

Primary Outcomes are change in total number of medications including the number of potentially inappropriate medications, number of medications associated with geriatric syndromes, and medications that contribute to anticholinergic and sedative drug burden.

Secondary Outcome is the impact of deprescribing on prevalence and severity of geriatric syndromes, medication adherence, and functional health status.

Eligible patient population is aged 50 years or older, experiencing polypharmacy as defined by 5 or more home medications, and hospitalized at VUMC with a referral to partner post-acute care facility.

Exclusion criteria include limited life expectancy (less than 6 months), non-English speaking, no telephone, homeless or incarcerated, enrolled in another drug trial, and expected to discharge from VUMC in less than 48 hours.

The primary study setting is Vanderbilt University Medical Center (VUMC), a private, non-profit, tertiary care teaching organization located in Nashville, Tennessee. The medical center is a principal referral center for physicians and patients throughout the Southeast, and it serves a diverse population in terms of income, geography, and education level. We will work with patients discharged to 20 SNFs and 2 IPRs within a nine-county radius of Nashville. The target PACs are all for-profit and comparable to PACs in the middle TN area based on publicly reported staffing and quality indicators ([www.medicare.gov](http://www.medicare.gov)).

The timeline for the study is 5 years with enrollment beginning in March 2017 and enrollment closing at the end of October 2020.

The Shed-MEDS intervention is a multistep deprescribing protocol which considers patient and disease factors, life expectancy, goals of care, and appropriate treatment targets. Medication-specific factors such as drug-drug interactions, drug-disease interactions, and drug-specific safety profiles are also incorporated. Finally, patient preferences and primary prescriber input are key to final deprescribing actions by identifying the medications patients are willing to discontinue and seeking their primary prescriber's agreement. In this intervention, deprescribing is defined as either stopping a medication or reducing the dose/frequency of a medication.

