Drug Burden Index (DBI): A DBI score is calculated separately for anticholinergic (DBIAC) and sedative medications (DBIS), which have been strongly linked to functional impairment, falls and delirium. The drug burden is the sum of each individual anticholinergic/sedative medication's prescribed daily dose divided by the sum of the minimum effective dose (as estimated by the FDA minimum recommended dose) and the patient's daily dose. The DBI includes over-the-counter medications. We will calculate the DBI at the time of randomization, hospital discharge, PAC discharge, and all follow-up timepoints. Importantly, the DBI captures reductions in dose, even when total number of medications is not reduced.

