## STATISTICAL CONSIDERATIONS

### Sample Size and Randomization

Figure 1 illustrates the flow of participants through the study and estimated total sample sizes during each study phase based on prior data. The overall effectiveness of the intervention will be evaluated based on the primary outcome measure, which is total medication count. Based on current enrollment rate, we estimate that approximately 144 patients per year will enroll in the study, or 576 across all four years of enrollment. Among those, we estimate that 27.5% will either die or otherwise be lost from the study prior to the 90-day post PAC discharge follow up period. Thus, across all four years of enrollment, an estimated 420 patients will contribute measurements at 90 days. Although 567 is the expected total enrollment, we conservatively use 420 to estimate the statistical power associated with the assessment of overall effectiveness (i.e., overall completion rate) rather than enrollment rate, to account for estimated attrition across all study phases.

Preliminary data is available for the effect of deprescribing on the reduction in the counts of total medications. Our pilot intervention (N=40) was associated with roughly a 50% reduction in the count of total medications from enrollment to hospital discharge, whereas a roughly 25% reduction was observed in the control group receiving routine hospital care. Using these preliminary data and mixed-effects Poisson regression methods, we implemented a simulation-based power analysis wherein we assumed that this effect would be attenuated by 20% at SNF discharge, and again by 20% at the 90-day follow up. Using a sample size of 420, there is greater than 95% power to detect a 50% versus 25% reduction in total medications. There is approximately 90% power to detect a 30% versus 25% reduction in total medications, and 80% power to detect a 27.5% versus 25% reduction in total medications. Thus, the target sample size provides some protection against effects that are substantially smaller than that observed in our preliminary data.

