## Outcomes

Hypotheses 1a-1b: The effect of the intervention on the total number of medications, PIMs, and medications associated with geriatric syndromes at hospital discharge, SNF discharge, and at 90-days following SNF discharge will be assessed using mixed effects Poisson regression, allowing for overdispersion (more or less variability than is expected under the Poisson regression model), and adjusting for measurement time point (as a categorical covariate) and the total number of medications at participant enrollment. The within-subject correlation among repeated measurements will be modeled using a random intercept term, indexed by subject. The intervention effect at each time point will be summarized using a Wald-type 95% confidence interval. Statistical significance will be indicated if the 95% confidence interval excludes the value zero (i.e., the Poisson regression intervention effect under the null hypothesis). Model fit will be assessed by examining the associated Pearson residuals and using other graphical methods. Alternative regression techniques may be used in the case of poor fit, for example, negative-binomial regression.

Hypothesis 1c: The effect of intervention on the anticholinergic and sedative medication drug burden scores at hospital discharge, SNF discharge, and 90-days following SNF discharge will be assessed using linear mixed effects regression, adjusting for measurement time point, and using a random intercept term indexed by subject. Intervention effects will be summarized using 95% confidence intervals. Model fit will be assessed using residual diagnostics and graphical methods. Due to the constrained nature of the score values (0-1 for anticholinergic and sedative drug burden scores), an alternative method may be required, such a ‘beta’ regression, which is suitable when such scores frequently occur at a boundary (0 or 1).

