Hypothesis 2a: The prevalence and severity of geriatric syndromes will be analyzed at each time point following SNF discharge. The effects of intervention on the prevalence of each type of geriatric syndrome will be assessed using mixed-effects logistic regression, adjusting for measurement time point (categorical). The severity of each geriatric syndrome is measured on an ordinal scale. Thus, severity will be analyzed using mixed-effects proportional odds logistic regression, also adjusting for measurement time point. For either method, the correlation among repeated measures will be modeled using a random intercept term indexed by subject. The effects of intervention at each time point will be summarized using the odds ratio with Wald-type 95% confidence intervals. Statistical significance will be indicated when the 95% confidence interval excludes the value one (i.e., null hypothesis value for both types of logistic regression). Model fit diagnostics and alternative analysis strategies will be considered as described for Hypotheses 1a-1c.

Hypothesis 2b: Patient medication adherence will be measured using selected questions from the ARMS, based on an ordinal scale. Functional health status will be measured using the VES-13 total score, which is also an ordinal outcome. The effects of intervention on these outcomes will be assessed at 7 and 90-days following SNF discharge using mixed-effects logistic regression or proportional odds logistic regression in a manner that is analogous to that described for Hypothesis 2a.

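### Hypothesis 1c treats the drug burden scores as lying between 0 and 1 and names beta regression for scores at 0 or 1, but the score as defined can exceed 1 and standard beta regression accepts neither boundary value

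*Combined protocol and SAP*

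**What the plan says.** The score is defined under Descriptions of Assessments, Primary Outcomes - Medications. Separate scores are calculated for anticholinergic and for sedative drugs. The text begins "The drug burden is the sum of each individual anticholinergic/sedative" and goes on to divide each drug's daily dose by that dose plus the minimum effective dose. Over-the-counter drugs count. No cap or rescaling is given. On timing: "We will calculate the DBI at the time of randomization, hospital discharge, PAC discharge, and all follow-up timepoints".

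The analysis is under Statistical Considerations, Outcomes, Hypothesis 1c. The effect on the two scores at hospital discharge, SNF discharge and 90 days "will be assessed using linear mixed effects regression, adjusting for measurement time point, and using a random intercept term indexed by subject". The plan continues: "Due to the constrained nature of the score values (0-1 for anticholinergic and sedative drug burden scores), an alternative method may be required". The example offered is beta regression, "which is suitable when such scores frequently occur at a boundary (0 or 1").

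On the standing of the outcome, Study Design includes "medications that contribute to anticholinergic and sedative drug burden" among the primary outcomes, and Table 1 places the DBI under the primary medication outcomes. Sample Size and Randomization, however, says: "The overall effectiveness of the intervention will be evaluated based on the primary outcome measure, which is total medication count".

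**The concern.** The definition and the analysis section disagree about the range of the same variable. A sum of terms that are each below 1 is not itself limited to 1, so the stated 0-1 range holds only for patients with few drugs in the class.

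The alternative method is also said to suit a situation that it cannot handle. The beta distribution is defined on the open interval between 0 and 1. A score of exactly 0 is ordinary here: it means that the patient takes no drug of that class, which is a result the intervention tries to bring about.

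If the residuals show that the linear mixed model fits badly, the one alternative named cannot be fitted to the scores as defined. The replacement would then be chosen with the data in hand, for an outcome listed among the primary ones.

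A separate, smaller point concerns the same model. H1c adjusts only for time point, although the DBI is measured at randomization and the models for Hypotheses 1a-1b adjust for the medication count at enrollment.

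**Working it through.** **Range of the score.** Let D be a drug's daily dose, M its minimum effective dose, and x = D/M. One drug contributes D/(M + D) = x/(1 + x), which is always below 1. For k drugs of one class, all at ratio x, DBI = k·x/(1 + x):

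- k = 1, x = 1: 0.50
- k = 2, x = 0.5: 0.67
- k = 2, x = 1: 1.00
- k = 2, x = 2: 1.33
- k = 3, x = 0.5: 1.00
- k = 3, x = 1: 1.50
- k = 3, x = 2: 2.00

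The plan's 0-1 range is therefore not reproduced. The score exceeds 1 from four drugs at x = 0.5, three at x = 1 and two at x = 2. Zero is a real boundary. One is not: a single drug never reaches it and several drugs pass through it.

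**Other readings of the definition.** If each dose were divided by that dose plus the sum of all minimum doses, three drugs at x = 2 would give 3 × 2/(3 + 2) = 1.20, again above 1. Only a pooled ratio, total dose over total minimum dose plus total dose, stays below 1. That ratio adds doses of different drugs. With all drugs at the same x it equals x/(1 + x) whatever the number of drugs, and it never equals 1, so it does not match the plan's mention of scores at 1 either.

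**Beta regression.** With shape parameters a and b, the log-likelihood of a score y contains (a − 1)·log(y) + (b − 1)·log(1 − y). At y = 0 or y = 1 this is infinite or undefined; above 1 the term log(1 − y) does not exist. A standard routine (statsmodels 0.14.6, BetaModel) given 200 valid values plus a single 0, 1 or 1.33 refused the data in all three cases. A zero/one-inflated beta model would accept 0 and 1 but not values above 1, and the plan does not name it.

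**How many scores are affected.** The documents give no DBI distribution, so this is an illustration. Assume that the number of drugs per class is Poisson with mean 1, 1.5 or 2, and that doses are all 0.5, 1 or 2 times the minimum, or an equal mix of the three (mix simulated with 400,000 patients). The share outside (0,1) is P(DBI = 0) + P(DBI ≥ 1). For mean 1 at half dose: 0.368 + 0.080 = 0.448.

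| Mean drugs | Exactly 0 | Outside (0,1): x = 0.5 | x = 1 or 2 | Mixed doses | Above 1: x = 0.5 | x = 1 | x = 2 |
|---|---|---|---|---|---|---|---|
| 1 | 36.8% | 44.8% | 63.2% | 57.1% | 1.9% | 8.0% | 26.4% |
| 1.5 | 22.3% | 41.4% | 66.5% | 58.2% | 6.6% | 19.1% | 44.2% |
| 2 | 13.5% | 45.9% | 72.9% | 64.0% | 14.3% | 32.3% | 59.4% |

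**Baseline DBI.** For a comparison at a single time point, adjusting for a baseline value with correlation r multiplies the variance of the treatment effect by 1 − r². Assumed r = 0.3, 0.5 and 0.7 give 0.91, 0.75 and 0.51. The random intercept does not do this job, because every outcome time point listed for H1c comes after randomization.

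**The case against.** The strongest reply is that nothing the plan is bound to do fails. The committed analysis is the linear mixed model, which accepts zeros and values above 1. Beta regression is conditional and offered as an example, much as negative-binomial regression is for H1a-1b. The Repeated measures paragraph under Data Analyses also allows an alternative method with sandwich standard errors. All of this is true and limits the consequence. That paragraph names no model, though, so it does not fill the gap.

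It can also be said that choosing a model after seeing the data is already built into the plan's tentative wording, whatever the range. That stands too: naming a better model is not enough unless the plan also says when it is used.

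The magnitudes are assumed, and the 41-73% range depends on the values chosen; a Poisson mean of 3 at double dose would give 85%. Part of it is exact ones from drugs all at the same dose level: at x = 1, 18 to 27 percentage points. Only values strictly above 1 show the conflict over the range, and 2% to 59% is too wide to say how common they are. The argument does not need a frequency, since one such value stops the fit.

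The baseline covariate is a question of precision. Leaving it out of a randomized comparison is not an error; H2a and H2b state no baseline adjustment either, and H1a-1b adjust for total count rather than for each outcome's own baseline. It should be weighed separately.

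Finally, the Study Design wording may describe a count of drugs rather than the DBI score. The DBI is nevertheless placed under the primary medication outcomes both in Table 1 and in the assessment descriptions.

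**Conclusion.** The concern holds. On the protocol's own definition the scores start at 0 and have no ceiling at 1, and standard beta regression cannot be used in the situation for which the plan calls it suitable. Neither conclusion rests on an assumption about the data. How often it matters does: between 41% and 73% of scores outside the open interval under the assumed drug counts and doses, with the true share unknown. The sponsor could find out from the pilot, which recorded the DBI in both groups at hospital discharge.

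The effect is confined to H1c and to its fallback. The first-choice model, the sample size and the power calculation for total medication count are untouched. It is worth correcting before analysis, but it does not threaten the trial's main result. Adding baseline DBI is a separate improvement in precision, whose size depends on a correlation that the documents do not give.

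**What to change.** Reconcile the DBI definition with the Hypothesis 1c text.

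If the sum as defined is intended:

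- State the range as 0 upward, with no cap at 1.
- Keep the linear mixed model as the main H1c analysis and add each participant's baseline value of the same DBI score as a covariate.
- Replace beta regression with one prespecified model that allows exact zeros and values above 1. Hypothesis 2a already provides one, where "severity will be analyzed using mixed-effects proportional odds logistic regression"; a Tweedie or two-part mixed model would also serve.
- State which diagnostic finding triggers the fallback, or report it in every case as a sensitivity analysis.

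If a score rescaled to 0-1 is intended, define the rescaling where the DBI is defined and name zero/one-inflated beta regression.

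The cost is wording only: baseline DBI is already collected, the sample size does not change and standard software suffices. The one drawback is that the fallback reports its effect on a different scale (an odds ratio for proportional odds), or in two parts for the two-part model.

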**Specific Aim 2:** Document the effects of the patient-centered deprescribing intervention (Shed-Meds) on geriatric syndromes, medication adherence, and health status.

[figure not shown]
**Hypothesis 2a:** Shed-Meds will result in a significantly lower prevalence and severity of geriatric syndromes 90 days after SNF discharge.

**Hypothesis 2b:** Shed-Meds will result in a significant improvement in medication adherence and self-rated health status after SNF discharge.

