Pressure Ulcers: The presence of pressure ulcers (Stages 0 – 4) will be abstracted from the hospital medical record (flowsheets) at baseline and confirmed via direct interview with the patient and/or family. Similarly, this same information will be, again, abstracted from the PAC medical record and confirmed via patient/family interview during an in-person visit 7 and 90-days post PAC discharge.

Adherence to Refills and Medications Scale (ARMS): The ARMS consists of 12 items to assess overall medication adherence, with a total score range of 12 to 48. A lower score is indicative of better medication adherence. Example questions include: “How often do you forget to take your medicines?”, “How often do you miss taking your medicines when you feel better?”, and “How often do you put off refilling your medicines because they cost too much money?” Response options are on a 4-point Likert scale that ranges from “none of the time” to “all of the time.”

Vulnerable Elders Survey (VES-13) is a functional measure of health status that assesses a patient’s cognitive, physical and self-care activities and which also includes an item for self-rated health status. Scores range from 1 to 10, with lower scores indicative of better health.

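### The adherence endpoint is an unnamed subset of ARMS questions, although the protocol describes a 12-item total; make the total the endpoint and align its visits with Table 1

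*Combined protocol and SAP*

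**What the plan says.** Hypothesis 2b expects that "Shed-Meds will result in a significant improvement in medication adherence and self-rated health status after SNF discharge".

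Under Descriptions of Assessments, the instrument is introduced as follows: "The ARMS consists of 12 items to assess overall medication adherence, with a total score range of 12 to 48". The direction is given ("A lower score is indicative of better medication adherence") and so is the item format ("Response options are on a 4-point Likert scale").

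Under Statistical Considerations, Outcomes, the Hypothesis 2b paragraph begins: "Patient medication adherence will be measured using selected questions from the ARMS, based on an ordinal scale". It continues: "Functional health status will be measured using the VES-13 total score, which is also an ordinal outcome". Both outcomes are to be compared between groups at 7 and 90 days after SNF discharge, "using mixed-effects logistic regression or proportional odds logistic regression in a manner that is analogous to that described for Hypothesis 2a". The significance rule brought over from Hypothesis 2a is: "Statistical significance will be indicated when the 95% confidence interval excludes the value one". No multiplicity control is stated for these outcomes.

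Table 1 (Schedule of Assessments) lists the ARMS without any mention of a subset. As extracted, its row carries marks at baseline, 60 days and 90 days, and none at 7 days.

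**The concern.** The two sections do not describe the same endpoint. One gives a scale with a defined total. The other gives an unspecified part of that scale with no scoring rule and no reason for setting the total aside. Nowhere else in the documents are the selected questions named.

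This leaves three things open at once: the items, how they are combined, and the model (binary logistic or proportional odds, hence possibly a cut-point as well). An adherence result reported under this plan could not be checked against a pre-specified definition, and a reader could not rule out that the items were picked because they showed a difference.

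The visits add a second inconsistency: the 2b paragraph calls for a 7-day adherence comparison for which Table 1 shows no ARMS data.

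**Working it through.** **1. What the described total is.** With 12 items on a 4-point scale scored 1 to 4, the range is 12 × 1 = 12 to 12 × 4 = 48. This reproduces the stated range, so the described total uses all 12 items. A sum of fewer items scored this way cannot have that range.

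**2. Adherence and functional health in the same paragraph.**

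| | ARMS | VES-13 |
|---|---|---|
| Analysed quantity | selected questions, not named | total score |
| Visits in the 2b analysis | 7 and 90 days | 7 and 90 days |
| Visits in Table 1, as extracted | baseline, 60, 90 days | baseline, 7, 90 days |

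The 7 and 90 day visits fit the VES-13 schedule but not the ARMS schedule.

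**3. Size of the selection problem, if single items were tested.** Inputs: 12 items (assessment description) and a two-sided 0.05 level per test (95% interval rule). For independent items at one visit:

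1 − (1 − 0.05)^12 = 1 − 0.95^12 = 0.46.

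Items of one scale are normally correlated. The documents give no inter-item correlation, so a range was assumed. The chances below come from 400,000 simulated sets of 12 equally correlated test statistics under no effect.

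| Assumed correlation | At least one item significant, either direction | At least one item significant, favouring intervention |
|---|---|---|
| 0 | 0.46 | 0.26 |
| 0.2 | 0.43 | 0.22 |
| 0.3 | 0.40 | 0.20 |
| 0.4 | 0.36 | 0.18 |
| 0.5 | 0.32 | 0.16 |

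The nominal values are 0.05 for either direction and 0.025 for benefit. If instead a summed subset of any size could be chosen freely, the chance of a false benefit is 0.36 to 0.20 at correlations of 0.2 to 0.5. One pre-specified total is one test at 0.05 per visit.

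**4. Precision, as an illustration only.** The documents give no reliability, standard deviation or expected effect for the ARMS. Assume parallel items and a 12-item reliability R of 0.7 to 0.9. By Spearman-Brown, single-item reliability is r = R / (12 − 11R), and for k items it is k·r / (1 + (k − 1)·r). The sample size needed relative to the total is R divided by that value.

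- R = 0.7: r = 0.7 / 4.3 = 0.163. Three items give 0.368, so the ratio is 0.7 / 0.368 = 1.9. One item gives 0.7 / 0.163 = 4.3.
- R = 0.9: r = 0.9 / 2.1 = 0.429. Three items give 0.692, so the ratio is 0.9 / 0.692 = 1.3. One item gives 0.9 / 0.429 = 2.1.

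The direction is what one would expect. The size depends on the assumptions.

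**The case against.** Several stronger readings are tempting, and the documents do not support them.

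- **That each item gets its own ordinal model.** The text does not say so. Calling the VES-13 also an ordinal outcome suggests that adherence is meant as one ordinal outcome, perhaps a summed subset. The figures in step 3 apply only if the reading is single items, or a free choice of subset.
- **That the sponsor will choose items after seeing the data.** Selected may equally mean fixed when the questionnaire was built. The text shows only that the choice is not recorded.
- **That 46% is the error rate of the plan.** It is the ceiling for single-item testing at one visit. It needs 12 separate, independent tests and counts results in the wrong direction.
- **That all 12 items are certainly on file.** The assessment section describes the instrument, and Table 1 names it. Full administration is implied but not stated, and the 2b sentence could mean that only some questions were asked.
- **That loss of precision is demonstrated.** If deprescribing moved only a few behaviours, a well-chosen subset fixed in advance could be as sensitive as the total, or more so. The example questions range from forgetting doses to delaying refills because of cost, so a uniform response is not assured.

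It is also fair to say that adherence is one of many secondary outcomes, and that overall effectiveness is judged on total medication count.

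What stands is that the endpoint is undefined where it is analysed and differs from the one described where it is measured. The case for a subset is a reason to name the subset, not to leave it open.

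**Conclusion.** The point holds as a specification defect with a specific remedy. The analysis section replaces a defined 12-item total with an unnamed, unscored subset, while treating the neighbouring VES-13 by its total. The exposure is conditional: at most 0.46, and about 0.43 to 0.32 at assumed correlations of 0.2 to 0.5, for at least one false-positive item at one visit, if single items were tested and picked after the data were seen. A subset is probably less precise than the total, but the documents do not allow the loss to be computed. The ARMS visits in the analysis also conflict with Table 1 as extracted. The primary conclusion and the sample size are unaffected.

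**What to change.** In the Hypothesis 2b paragraph:

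1. Name the ARMS 12-item total (12 to 48, lower better) as the single adherence endpoint, analysed with the mixed-effects proportional odds model. Drop the binary logistic alternative for it. Report single items descriptively.
2. Adjust for the baseline ARMS total. Table 1 shows a baseline ARMS, but the 2a and 2b models adjust only for time point. The plan already adjusts for an enrolment value, the total medication count, under Hypotheses 1a-1b. State how a missing baseline is handled: the ARMS is not among the assessments that surrogates may complete (Study Procedures), so patients with delirium or cognitive impairment may lack one.
3. Give the ARMS analysis visits as 60 and 90 days to match Table 1, and leave 7 and 90 days for the VES-13.
4. If only some items were administered, list those items and define their summed score before unblinding, and correct the assessment description to match.

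The cost is a few sentences. No new data are needed if all 12 items were administered. If they were not, item 4 is the available remedy and costs no more.
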